9 STATISTICAL ANALYSIS PLAN

This section outlines the statistical analysis strategies and procedures for the primary and secondary analyses of the study. Exploratory and other nonconfirmatory analyses will be outlined in a separate sSAP.

If, after the study has begun, changes are made to primary and/or secondary objectives, or the statistical methods related to those objectives, then the protocol will be amended (consistent with ICH Guideline E9). Changes to exploratory or other nonconfirmatory analyses made after the protocol has been finalized, but prior to the conduct of any analyses, will be documented in the sSAP as needed and referenced in the CSR for the study. ^{CCI}

CCI

9.1 Statistical Analysis Plan Summary

Key elements of the SAP are summarized. The comprehensive plan is provided in Sections 9.2 through 9.12.

Study Design Overview	This is a randomized, active-controlled, parallel group, multicenter, open-label, Phase 2 study of IT MK-1454 in combination with pembrolizumab IV versus pembrolizumab IV monotherapy in participants with a histologically or cytologically confirmed diagnosis of metastatic, or unresectable, recurrent HNSCC with a tumor CPS ≥ 1 as first-line therapy.
Intervention Assignment	Approximately 200 participants will be randomized in a 1:1 ratio to Arm 1 (IT MK-1454 plus pembrolizumab IV) and Arm 2 (pembrolizumab IV). The stratification factors are PD-L1 expression level defined by CPS (≥ 1 to < 20 vs ≥ 20), ECOG performance status (0 versus 1) and HPV status (positive, negative for participants with oropharyngeal cancer).
Analysis Populations	Efficacy (Primary and Secondary): ITT Safety (Secondary): APaT
Primary Endpoint(s)	OR is a confirmed CR or PR) by RECIST 1.1 as assessed by BICR.
Secondary Endpoints	
• PFS by RECIST 1.1 as assessed by BICR• DOR by RECIST 1.1 as assessed by BICR• OS• AEs• Discontinuing study intervention due to AE

Statistical Methods for Key Efficacy Analyses
	
The dual primary hypotheses comparing Arm 1 to Arm 2 for participants with CPS ≥ 1 and CPS ≥ 20 with regard to ORR will be evaluated using the stratified Miettinen and Nurminen method [Miettinen, O. and Nurminen, M. 1985]. The difference in ORR will be estimated using the stratified Miettinen and Nurminen method with strata weighting by sample size.

Statistical Methods for Key Safety Analyses
	
The analysis of safety results will follow a tiered approach for the comparison of Arm 1 versus Arm 2. The tiers differ with respect to the analyses that will be performed. There is no Tier 1 safety endpoint for this study. Tier 2 parameters will be assessed via point estimates with 95% CIs provided for between-arm comparisons; only point estimates by treatment arm are provided for Tier 3 safety parameters. The 95% CIs for the between-treatment differences in percentages will be provided using the Miettinen and Nurminen method [Miettinen, O. and Nurminen, M. 1985].

Interim Analyses
	
CCI


Multiplicity
	
The overall type I error rate for the primary endpoint (OR) CCI will be strongly controlled at $\alpha = 2.5\%$ (one-sided) [Chen, C., et al 2018].
 
CCI
 
CCI $\alpha = 1\%$ (one-sided) will be allocated to ORR in participants with CPS ≥ 1 and $\alpha = 1.5\%$ (one-sided) will be allocated to ORR in participants with CPS ≥ 20. The graphical approach of Maurer and Bretz [Maurer, W. and Bretz, F. 2013] will be applied to reallocate alpha between the dual primary hypotheses if either primary hypothesis is rejected.
 
CCI

Sample Size and Power	
The overall sample size will be approximately [CCI] 200, [CCI]
 
[CCI]
 
[CCI]
 
[CCI] it provides approximate 84.0% power to detect a 21% difference in ORR (40% in Arm 1 versus 19% in Arm 2) at the type I error of 1% (one-sided) for participants with $CPS \geq 1$. Based on MK-3475 KN048 data, the prevalence rate of the participants with $CPS \geq 20$ among participants with $CPS \geq 1$ is assumed to be 50%. With 50 participants per arm, the study has approximately 86.3% power to detect a 31% difference in ORR (55% in Arm 1 versus 24% in Arm 2) at the type I error of 1.5% (one-sided) for participants with $CPS \geq 20$. It has approximately 91.5% power to show that Arm 1 is superior to Arm 2 in at least 1 population (participants with $CPS \geq 1$ or participants with $CPS \geq 20$) at an overall type I error of 2.5% (one-sided).
 
[CCI]

------------------------------	---

9.2 Responsibility for Analyses/In-house Blinding

The statistical analyses of the data obtained from this study will be the responsibility of the Clinical Biostatistics department of the Sponsor.

The Sponsor will generate the randomized allocation schedule(s) for study treatment assignment for this protocol, and the randomization will be implemented in IRT.

Although the study is an open-label study, analyses or summaries generated by randomized treatment assignment, and actual treatment received will be limited and documented. Further documentation will be provided in the sSAP. In addition, independent radiologist(s) will perform the central imaging review without knowledge of treatment assignments.

[CCI]

9.3 Hypotheses/Estimation

Objectives and hypotheses of the study are outlined in Section 3.

9.4 Analysis Endpoints

9.4.1 Efficacy/Immunogenicity/Pharmacokinetics Endpoints

Primary Efficacy Endpoint

- OR: a confirmed CR or PR per RECIST 1.1 based on BICR. ORR is the proportion of participants with objective response.

Secondary Efficacy Endpoints

- PFS: time from randomization to the first documented PD per RECIST 1.1 based on BICR or death from any cause, whichever occurs first. See Section 9.6.1 for the definition of censoring.
- DOR: time from the first documented evidence of CR or PR until PD per RECIST 1.1 as assessed by BICR or death due to any cause, whichever occurs first, in participants demonstrating CR or PR.
- OS: time from randomization to the date of death due to any cause.

CCI

9.4.2 Safety Endpoints

Safety endpoint is the number/proportion of participants with AEs, and who discontinue study treatment due to AEs. In addition, safety and tolerability will be assessed by clinical review of all relevant parameters including AEs, laboratory tests, and vital signs.

A description of safety measures is provided in Section 8.3 Safety Assessments.

9.5 Analysis Populations

9.5.1 Efficacy Analysis Populations

The analyses of efficacy endpoints (ORR, PFS, and OS) are based on the ITT population. All randomized participants will be included in this population. Participants will be analyzed in the treatment arm to which they are randomized. For the analysis of DOR, only participants with a CR or PR in the ITT population will be included.

A supportive approach using a modified ITT population may be performed for the efficacy endpoints. The modified ITT population consists of all randomized participants who receive scheduled treatments without substantial dose interruption as defined in the sSAP. These details will be documented in the sSAP.

9.5.2 Safety Analysis Populations

The APaT population will be used for the analysis of safety data in this study. The APaT population consists of all randomized participants who receive at least 1 dose of study treatment. Participants will be analyzed in the treatment arm corresponding to the study treatment they actually receive. For most participants, this will be the treatment group to which they are randomized. Participants who receive incorrect study treatment for the entire treatment period will be included in the treatment arm corresponding to the study treatment actually received. Any participant who receives incorrect study medication for 1 cycle, but receives the correct treatment for all other cycles, will be analyzed according to the correct treatment group, and a narrative will be provided for any events that occur during the cycle for which the participant is incorrectly dosed.

At least 1 laboratory or vital sign measurement obtained subsequent to at least 1 dose of study treatment is required for inclusion in the analysis of each specific parameter. To assess change from baseline, a baseline measurement is also required.

CCI

9.6 Statistical Methods

This section describes the statistical methods that address the primary and secondary objectives. Methods related to exploratory endpoints will be described in the sSAP.

9.6.1 Statistical Methods for Efficacy Analysis

Efficacy results that will be deemed to be statistically significant after consideration of the Type I error control strategy are described in Section 9.8. Nominal p -values will be computed for other efficacy analyses but should be interpreted with caution due to potential issues of multiplicity. For the stratified analyses, if the number of participants or events in a cell is small, the stratification factor(s) may be removed.

9.6.1.1 Objective Response

The stratified Miettinen and Nurminen method [Miettinen, O. and Nurminen, M. 1985] will be used for the ORR comparison (Arm 1 vs Arm 2) in participants with CPS ≥ 1 and in participants with CPS ≥ 20 . The difference in ORR, 95% CI and p -values from the stratified

Miettinen and Nurminen method [Miettinen, O. and Nurminen, M. 1985] with strata weighting by sample size will be reported. The stratification factor used for randomization (Section 6.3.2) will be applied to the analysis. In the IA for continuing enrollment decision-making, the stratification will be based on PD-L1 CPS (≥ 1 to < 20 vs ≥ 20). Sensitivity analyses will be performed for comparison of ORR based on the investigator's assessment.

9.6.1.2 Progression-free Survival

The nonparametric Kaplan-Meier method [Kaplan, E. L. 1958] will be used to estimate the PFS curve for each treatment group in participants with CPS ≥ 1 and in participants with CPS ≥ 20 . The treatment difference in PFS will be assessed by the stratified log-rank test. A stratified Cox proportional hazard model [Cox, D. R. 1972] with Efron's method [Efron, B. 1977] of tie handling will be used to assess the magnitude of the treatment difference (ie, the HR) between the treatment arms. The HR and its 95% CI from the stratified Cox model with Efron's method of tie handling and with a single treatment covariate will be reported. The stratification factor used for randomization (Section 6.3.2) will be applied to both the stratified log-rank test and the stratified Cox model.

Because disease progression is assessed periodically, PD can occur any time in the interval between the last assessment when PD is not documented and the assessment when PD is documented. For the primary analysis, for participants with PD, the true date of disease progression will be approximated by the date of the first assessment at which PD is objectively documented per RECIST 1.1, based on BICR. Death is always considered as a confirmed PD event. Participants who do not experience a PFS event will be censored at the last disease assessment. Sensitivity analyses will be performed for comparison of PFS based on the investigator's assessment.

In order to evaluate the robustness of the PFS endpoint per RECIST 1.1 by BICR, 1 primary and 2 sensitivity analyses with a different set of censoring rules will be performed. For the primary analysis, if the events (PD or death) are immediately after more than 1 missed disease assessment, the data are censored at the last disease assessment prior to the missed visits. Also, data after new anticancer therapy are censored at the last disease assessment prior to the initiation of new anticancer therapy. The first sensitivity analysis follows the ITT principle. That is, PDs/deaths are counted as events regardless of missed study visits or initiation of new anticancer therapy. The second sensitivity analysis considers initiation of new anticancer treatment or discontinuation of treatment due to reasons other than CR to be a PD event for participants without documented PD or death. If a participant meets multiple criteria for censoring, the censoring criterion that occurs earliest will be applied. The censoring rules for primary and sensitivity analyses are summarized in [Table 11](#).

In case there is an imbalance between the treatment groups on disease assessment schedules or censoring patterns, we may also perform a sensitivity analysis for PFS using interval censored data [Finkelstein, D. M. 1986], which modifies the Cox proportional hazard model for interval censored data. The interval will be constructed so that the left endpoint is the date of the last disease assessment without documented PD and the right endpoint is the date of documented PD or death, whichever occurs earlier.

Table 11 Censoring Rules for Primary and Sensitivity Analyses of PFS

Situation	Primary Analysis	Sensitivity Analysis 1	Sensitivity Analysis 2
PD or death documented after ≤ 1 missed disease assessment, and before new anticancer therapy, if any	Progressed at date of documented PD or death	Progressed at date of documented PD or death	Progressed at date of documented PD or death
PD or death documented immediately after ≥ 2 consecutive missed disease assessments or after new anticancer therapy, if any	Censored at last disease assessment prior to the earlier date of ≥ 2 consecutive missed disease assessments and new anticancer therapy, if any	Progressed at date of documented PD or death	Progressed at date of documented PD or death
No PD and no death; new anticancer treatment is not initiated	Censored at last disease assessment	Censored at last disease assessment	Progressed at treatment discontinuation due to reasons other than CR; otherwise censored at last disease assessment if participant is still receiving study treatment or has completed study treatment
No PD and no death; new anticancer treatment is initiated	Censored at last disease assessment before new anticancer treatment	Censored at last disease assessment	Progressed at date of new anticancer treatment
PD progressive disease; PFS progression free survival.			

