2.2.3.2 Pembrolizumab (MK-3475) Clinical Studies

Pembrolizumab is approved as monotherapy in patients whose tumors express PD-L1 CPS ≥ 1 or in combination with platinum and fluorouracil, a standard chemotherapy regimen, for the first-line treatment of patients with metastatic or with unresectable, recurrent HNSCC. Refer to the IB/approved local product label for list of approvals for pembrolizumab. The approval is based on results from a prespecified IA of the Phase 3 KEYNOTE-048 study, a randomized, multicenter, open-label, active-controlled study conducted in 882 patients with metastatic HNSCC who had not previously received systemic therapy and who were considered incurable by local therapies.

Among the 882 patients, the study population characteristics were: median age of 61 years (range, 20 to 94), 36% age 65 or older; 83% male; 73% white, 20% Asian, and 2.4% black; 61% had ECOG performance status of 1; and 79% were former or current smokers. Twenty-two percent of patients' tumors were HPV-positive; 23% had PD-L1 TPS $\geq 50\%$; and 95% had stage IV disease (19% were stage IVA, 6% were stage IVB, and 70% were stage IVC). Eighty-five percent of patients' tumors had PD-L1 expression of CPS ≥ 1 , and 43% had CPS ≥ 20 . The median duration of exposure to pembrolizumab 200 mg Q3W was 3.5 months (range, 1 day to 24.2 months) in the monotherapy arm and was 5.8 months (range, 3 days to 24.2 months) in the combination arm.

The main efficacy outcome measures were OS and PFS as assessed by BICR according to RECIST v1.1 (modified to follow a maximum of 10 target lesions and a maximum of 5 target lesions per organ) sequentially analyzed in the subgroup of patients with CPS ≥ 20 , the subgroup of patients with CPS ≥ 1 and the overall population.

Pembrolizumab demonstrated a significant improvement in OS compared with the EXTREME regimen (cetuximab with carboplatin or cisplatin plus fluorouracil), as monotherapy in patients whose tumors expressed PD-L1 (CPS ≥ 1) with a median OS of 13.6 months versus 10.4 months, respectively; (HR 0.65 [95% CI, 0.53-0.80]; p 0.00002) and in combination with chemotherapy in the total study population (HR 0.77 [95% CI, 0.63-0.93]; p 0.0067).

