Among participants whose tumors were CPS ≥ 20 , OS was also significantly improved in those treated with pembrolizumab plus chemotherapy versus the EXTREME regimen: HR 0.60 (95% CI, 0.45, 0.82); p 0.00044. Assessment by HPV status (participants with oropharyngeal cancer) indicated that among those who were HPV-positive, pembrolizumab plus chemotherapy showed clear improvement; median OS was 23.9 months (95% CI: 16.2, 34.5) compared with 15.9 months for standard treatment HR 0.56 (95%CI: 0.36, 0.87). Assessment of OS by the ECOG subgroups were consistent with the CIs of the primary findings overlapping the primary HR outcome CI.

Pembrolizumab was discontinued for adverse reactions in 12% of patients in the monotherapy arm. The most common adverse reactions resulting in permanent discontinuation of pembrolizumab were sepsis (1.7%) and pneumonia (1.3%). Adverse reactions leading to the interruption of pembrolizumab occurred in 31% of patients; the most common adverse reactions leading to the interruption of pembrolizumab ($\geq 2\%$) were pneumonia (2.3%), pneumonitis (2.3%) and hyponatremia (2%). The most common adverse reactions ($\geq 20\%$) with pembrolizumab as monotherapy were fatigue (33%), constipation (20%), and rash (20%).

Pembrolizumab is approved for use in the treatment of multiple tumor types [U.S. Prescribing Information 2019], and ongoing clinical studies with pembrolizumab are being conducted in multiple solid tumors. In addition, multiple combinations with pembrolizumab are also being investigated. Refer to pembrolizumab IB for study details.

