8.1.5.2 Concomitant Medications

The investigator or qualified designee will record medication, if any, taken by the participant during the study.

All medications related to reportable SAEs and ECIs should be recorded, as defined in Section 8.4.

All new anticancer therapy initiated after the study start must be recorded in the eCRF. If a participant initiates another anticancer therapy other than the assigned study intervention(s), the study intervention(s) should be discontinued, and the participant will move into the Survival Follow-up Phase. If a participant initiates a new anticancer therapy within 30 days after the last dose of the study intervention, the 30-day Safety Follow-up Visit is to occur before administration of the first dose of the new therapy.

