8.2.3 Tumor Imaging During the Study

The first on-study imaging assessment should be performed at 6 weeks (42-49 days) from the date of first dose. Subsequent tumor imaging should be performed every 6 weeks (42 days \pm 7 days) (or more frequently if clinically indicated). After 1 year, participants who remain on treatment will have imaging performed every 9 weeks (63 days \pm 7 days). Imaging timing should follow **calendar days** and should not be adjusted for delays in cycle starts. Imaging should continue to be performed until disease progression is identified by the investigator, the start of new anticancer treatment, withdrawal of consent, or death, or notification by the Sponsor, whichever occurs first. All supplemental imaging must be submitted to the iCRO.

Objective response should be confirmed by a repeat imaging assessment. Tumor imaging to confirm PR or CR should be performed at least 4 weeks after the first indication of response is observed. Participants will then return to regularly scheduled imaging, starting with the next scheduled imaging time point. Participants who receive additional imaging for confirmation do not need to undergo the next scheduled tumor imaging if it is less than 4 weeks later; tumor imaging may resume at the subsequent scheduled imaging time point. Note: Response does not typically need to be verified in real time by the BICR.

Per iRECIST (Section 8.2.5), disease progression should be confirmed by the site 4 to 8 weeks after site-assessed first radiologic evidence of PD in clinically stable participants. Participants who have unconfirmed disease progression may continue on treatment at the discretion of the investigator until progression is confirmed, provided they have met the conditions detailed in Section 8.2.5. Participants who receive confirmatory imaging do not need to undergo the next scheduled tumor imaging if it is less than 4 weeks later; tumor imaging may resume at the subsequent scheduled imaging time point, if clinically stable. Participants who have confirmed disease progression by iRECIST, as assessed by the site, will discontinue the treatment. Exceptions are detailed in Section 8.2.5.

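### PFS Sensitivity Analysis 2 dates a switch to new therapy by what happens afterwards, so a participant who switches and later dies is credited with longer PFS than one who switches and survives

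*Combined protocol and SAP*

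**What the plan says.** Section 9.6.1.2 plans one primary PFS analysis and two sensitivity analyses, SA1 and SA2. SA2 takes starting "new anticancer treatment or discontinuation of treatment due to reasons other than CR to be a PD event for participants without documented PD or death". The SA2 column of Table 11 carries this out:

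- Rows 1 and 2 (PD or death is documented; row 2 includes PD or death after new therapy): "Progressed at date of documented PD or death". The SA1 cells are the same.
- Row 3 (no PD, no death, no new therapy): "Progressed at treatment discontinuation due to reasons other than CR; otherwise censored at last disease assessment". The censoring is for participants still on treatment or who have completed it.
- Row 4 (no PD, no death, new therapy started): "Progressed at date of new anticancer treatment".

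The section's rule about taking the earliest criterion is limited to censoring criteria. It does not choose between competing event dates.

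Two follow-up rules matter. When a participant starts another anticancer therapy, "the study intervention(s) should be discontinued, and the participant will move into the Survival Follow-up Phase" (Section 8.1.5.2), with survival contact every 12 weeks (Section 8.10.3.3). Imaging ends at new therapy or earlier: "Imaging should continue to be performed until disease progression is identified by the investigator" (Section 8.2.3).

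**The concern.** A time-to-event definition should fix the event date from what has happened up to that date. In SA2 a switch is a failure at the switch date for a participant still alive without PD at the cutoff, but not for one who later dies. Among participants with the same switch date, the worse outcome receives the longer PFS time.

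The situation is built into the design. Study drug must stop when new therapy starts, imaging ends and survival follow-up continues. The later documented event after a switch is therefore normally a death, and it moves the participant from row 4 to row 2. As deaths accrue, SA2 converges on SA1, because the two differ only for participants alive without documented PD at the cutoff. What is at stake is whether SA2 works as a separate robustness check on PFS.

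**Working it through.** **1. Table 11 applied to four participants.** All stop at month 3 for a reason other than CR, with no PD by central review (BICR). The cutoff is month 18. Entries are the SA2 event month.

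| After the stop | Row | As written | Rows 2 and 4 edited | Earliest date in every row |
|---|---|---|---|---|
| No switch, alive | 3 | 3 | 3 | 3 |
| No switch, death at 14 | 1 (or 2) | 14 | 14 | 3 |
| Switch at 5, alive | 4 | 5 | 3 | 3 |
| Switch at 5, death at 14 | 2 | 14 | 5 | 3 |

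As written, the two switchers differ by 14 − 5 = 9 months because one died. Editing rows 2 and 4 reduces this to 5 − 3 = 2 months, the interval from stop to switch. It does not change the second participant. Only the earliest date in every row removes the dependence on later outcome.

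**2. Size.** The plan gives no event count, power or hazard ratio (HR) for PFS, so there is no figure to reproduce. The following is an illustrative simulation (200,000 per arm, exponential times) comparing the rule as written with the earliest date in every row.

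*Inputs from Section 2.2.3.2, pembrolizumab alone:* "Pembrolizumab was discontinued for adverse reactions in 12% of patients in the monotherapy arm"; "The median duration of exposure to pembrolizumab 200 mg Q3W was 3.5 months", used here as the median time to first event; median OS 13.6 months. Treating survival as the sum of two exponential times, with λ₁ = ln2/3.5 = 0.198 and λ₂ = ln2/8.1 = 0.0856:

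S(13.6) = (0.198·e^(−2.693) subtracted in the form [0.198·e^(−1.164) − 0.0856·e^(−2.693)]) / (0.198 − 0.0856), where only the bracket is the numerator, ≈ 0.50.

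Median survival after the first event is therefore about 8.1 months; 6 to 12 was run.

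*Assumed:* 8% stop on investigator PD that BICR does not call (range 0 to 15%); half of adverse-reaction stoppers and all of that 8% switch one month later; 8% of first events are deaths; 18-month accrual.

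*Equal arms, 24-month cutoff:* 17% of participants (10 to 24% over the 0 to 15% range) are dated later than their first event, by a mean of 3.2 to 3.3 months. Median SA2 PFS is 4.1 months as written and 3.5 with earliest dating. The HR is 1.00 either way.

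*Assumed 22% adverse-reaction stops in Arm 1 against 12% in Arm 2, 24-month cutoff:*

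| Model | HR as written | HR, earliest date |
|---|---|---|
| A: stops take the place of PD (equal total hazard) | 0.94 to 0.95 | 0.99 to 1.00 |
| A, arms reversed | 1.06 | 1.00 |
| B: stops come on top of equal PD hazards | 1.06 to 1.07 | 1.12 to 1.13 |

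The Model B earliest-date value has a closed form: 0.88/0.78 = 1.128. For scale, with about 184 events in 200 participants the standard error of log HR is 2/√184 = 0.147. The Model A shift is log(0.945) = −0.057, about 0.4 of one standard error.

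**The case against.** The best defence is that SA2 is meant as an imputation. It keeps every observed PD and death and counts a stop or switch as failure only where SA1 would censor. Text and table agree, so a reader who infers a contradiction between them would be mistaken. That purpose is coherent, but it does not repair the ordering: the switch date is dropped for exactly the switchers who go on to die.

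A second objection stands in part. Stopping treatment is not withdrawal (Section 7.1), and participants who stop without PD continue imaging (Section 8.2.4). Earliest dating for stops would replace some observed BICR PD dates with stop dates. For switches this cost is slight, because imaging ends at new therapy.

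A third stands in full. Most simulation inputs are assumed. Median exposure is a loose proxy for time to first event, since treatment may continue past first radiologic PD (Section 8.2.5). Clinically stable participants also have confirmatory imaging 4 to 8 weeks after investigator PD, so BICR may have a further scan on which to call PD.

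A reader might infer that SA2 favours one arm, or that earliest dating always brings the HR nearer to 1. The documents support neither. The HR as written falls on either side of 1 depending on the model and on which arm has more stops, and in Model B the earliest-date rule moves it further from 1.

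**Conclusion.** The concern holds as a flaw in the SA2 dating rule: followed as written, event dates depend on later outcomes and order some participants wrongly. This rests on Table 11 alone and needs no assumption. The effect on the HR does rest on assumptions, and its size and direction cannot be determined from the documents; the simulated values are illustrative only. With arms alike in stops, switches and later survival the effect is about nil.

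This is a minor improvement to one sensitivity analysis of a secondary endpoint. A reader might infer that the PFS conclusion or the trial's main result is at risk. It is not: formal type I error control is described for ORR (Section 9.8), and ORR, primary PFS and SA1 do not use the rule. Dates would also move between data cuts if SA2 were run more than once, but the documents do not show that it will be.

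**What to change.** In the SA2 column of Table 11:

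- Row 2: *Progressed at the earliest of new anticancer therapy and documented PD or death.*
- Row 4: *Progressed at the earlier of new anticancer treatment and treatment discontinuation for reasons other than CR or completion.* The mention of completion keeps row 4 in line with row 3, which already censors completers.
- Section 9.6.1.2: end the qualifying clause with *without documented PD or death before that date*. If only rows 2 and 4 change, attach this to new therapy alone, so that the text does not run ahead of row 1.

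For a fully consistent rule, also let an earlier stop for reasons other than CR or completion set the date in rows 1 and 2, apply the amended clause to stops as well, and label SA2 a treatment-failure analysis. The price is that some BICR PD dates observed after a stop give way to the stop date, and the HR then reflects any arm difference in stops. SA1 keeps the observed dates.

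The cost is two or three table cells, one clause and one programming rule. No new data are needed: new anticancer therapy is recorded in the eCRF (Section 8.1.5.2), and the primary reason for discontinuation is already to be displayed (Section 9.6.3.1). If the sponsor prefers the present rule, the plan should say that dating by later outcome is intended and why.
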